8.7 Adjustment of Dose and/or Treatment Schedule

Adjustments of dose and/or treatment schedule should occur only on rare occasions. Up to 2 adjustments in the treatment schedule may be allowed for patients that are unable to tolerate the once weekly dose (for example if platelet counts fall below 75,000/mm³ as described in Section 8.6.3). Any proposed adjustment to treatment schedule or dose level must be discussed with, and approved by, the Study Medical Monitor prior to initiation. If the patient remains stable after adjustment, they may be cautiously returned to the original dose/regimen after consultation with the Study Medical Monitor.

Patients may be dose paused in response to adverse events after consultation with Study Medical Monitor.

8.8 Discontinuation of Study Treatment

A patient must permanently discontinue study treatment for any of the following:

- The patient becomes pregnant. Report the pregnancy according to instructions in Section 9.5.4
- The patient withdraws consent
- The patient experiences an adverse event that necessitates permanent discontinuation of study treatment
- The patient develops laboratory test abnormalities that meet any of the stopping rules listed in Section 8.6
- The patient experiences an AE that necessitates unblinding of the Investigator to the patient's treatment assignment

The reason for discontinuation of study treatment must be recorded in the CRF and source documentation.

Patients that discontinue from treatment are encouraged to remain in the study. Every effort should be made to complete the early termination visit and the EOT efficacy assessment followed by all post-treatment evaluation visits. If the patient declines to participate in the post-treatment evaluation visits, at a minimum, the early termination visit and EOT efficacy assessment procedures should be performed at the time of withdrawal (See Appendix A) and ideally within 14 days from the last dose of Study Drug. If early termination assessments are to be performed on a day with mNIS+7 EOT assessment, the mNIS+7 assessment should be performed first.

8.9 Withdrawal of Patients from the Study

Patients must be withdrawn from the study for any of the following:

- Withdrawal of consent
- The patient is unwilling or unable to comply with the protocol
- Patient receives liver transplant

Other reasons for withdrawal of patients from the study might include:

- At the discretion of the Investigator for medical reasons
- At the discretion of the Investigator or Sponsor for noncompliance
- Significant protocol deviation
- Administrative decision by the Investigator or Sponsor

All efforts will be made to complete and report the observations as thoroughly as possible up to the date of withdrawal. All information, including the reason for withdrawal from Study, must be recorded in the CRF.

Any patient who withdraws consent to participate in the study will be removed from further treatment and study observation immediately upon the date of request. Patients withdrawn for any reason should be encouraged to complete the EOT efficacy assessment and early termination study visit at the time of withdrawal (Appendix A).

For patients who receive a liver transplant, every effort should be made to complete the EOT efficacy assessment as soon as feasible after the transplant procedures (if possible within 6 weeks). After the EOT efficacy assessment and early termination visit is complete, patients should be withdrawn from the study.

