10.3 Populations

The Full Analysis Set will include all randomized patients who received at least 1 injection of Study Drug (ISIS 420915 or placebo) and who have at least 1 post-baseline efficacy assessment for the mNIS+7 score or Norfolk QOL-DN questionnaire total score.

The Safety Set will include all randomized patients who received at least 1 injection of Study Drug.

The Per-Protocol Set will include the subset of the Full Analysis Set that have received at least a certain percentage of the prescribed doses of Study Drug and that have no significant protocol deviations that would be expected to affect efficacy assessments. The detailed criteria will be specified and finalized prior to conducting the primary analysis (i.e., exact criteria to determine inclusion in or exclusion from the Per Protocol Set will be determined for each patient prior to conducting the primary analysis).

The Pharmacokinetic Set will include the subset of the Safety Set that has at least 1 evaluable PK result.

The ECHO subgroup will include the subset of the Safety Set that has at least 1 evaluable post baseline ECHO assessment and participated in the ECHO substudy. The CM-ECHO Set will include the subset of the Safety Set that has at least 1 evaluable post baseline ECHO assessment and had a diagnosis of TTR cardiomyopathy at study entry but are not in the ECHO subgroup, plus patients who participated in the ECHO subgroup.

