In this model, missing data are not explicitly imputed (except for the assessment level data imputation specified in Section 3.2.1.3). Instead, all available post-baseline assessments of the endpoint during the treatment period (which fall in the Week 35 and Week 66 visit windows) for subjects in the FAS are utilized and via modelling of the within subject correlation structure, the endpoint treatment differences (which are adjusted to take account of missing data) are derived. The estimation of treatment differences is based upon the assumption that the missing data follows a missing at random mechanism (i.e. the missingness of the observations may be dependent on the observed outcomes or covariates, but not on unobserved outcomes).

The unstructured (2x2) covariance model will be used to model the within patient errors, shared across treatments and small sample adjustments to standard errors and tests will be made following

the Kenward-Roger approach (Kenward, M. G. and Roger, J. H. (1997)). In the unlikely circumstance that there are convergence problems with the repeated measures mixed model, this will be explored. For example the SCORING=4 option could be used in the PROC MIXED statement in SAS. This makes SAS use Fisher scoring for the first 4 iterations. If the convergence problem cannot be resolved the unstructured covariance matrix will be replaced by the restricted unstructured covariance matrix (Type=UNR in SAS). This also specifies an unstructured covariance matrix but with a different parameterization.

The treatment contrast for both Week 35 and Week 66 will be estimated by the model, with the Week 66 estimate considered primary. The normality assumptions for the MMRM models will be formally tested using a Shapiro-Wilks test at the 0.01 significance level and assessed by inspection of the following plots:

- Histogram of marginal studentized residuals derived from the MMRM model.
- Normal probability plot.

If the Shapiro-Wilks test assessing normality of the MMRM residuals from week 66 is statistically significant at the 0.01 level, formal hypothesis testing for that endpoint will be done at the 0.025 one-sided significance level using a non-parametric rerandomization test. Thus, the null hypothesis for the endpoint will only be tested using the results from the MMRM if the p-value from the Shapiro-Wilks test is > 0.01.

Steps for the rerandomization test are:

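### Protocol 8.9 takes patients out of the study for compliance failures and deviations, so a patient still dosing and willing to be assessed can lose an obtainable Week 66 value

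*Protocol*

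**What the plan says.** Protocol 8.9 concerns leaving the study, as distinct from stopping Study Drug. Its mandatory list contains withdrawn consent, liver transplant and "The patient is unwilling or unable to comply with the protocol". A second list opens with "Other reasons for withdrawal of patients from the study might include" and includes "At the discretion of the Investigator or Sponsor for noncompliance" and "Significant protocol deviation", next to investigator discretion for medical reasons and administrative decisions. The section adds: "Patients withdrawn for any reason should be encouraged to complete the EOT efficacy assessment and early termination study visit at the time of withdrawal".

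Protocol 8.8, on stopping drug, says: "Patients that discontinue from treatment are encouraged to remain in the study". Protocol 6.1.2 lets patients who refuse PK or ECHO subgroup procedures stay on study.

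Under Protocol 10.3 and SAP 3.2.2, the Full Analysis Set (FAS) needs one injection and a post-baseline mNIS+7 or Norfolk QOL-DN assessment; the SAP adds a baseline. Neither document applies a compliance or deviation criterion to it. The Per-Protocol Set is limited to patients who "have no significant protocol deviations that would be expected to affect efficacy assessments", and the SAP adds receipt of at least 80% of prescribed doses.

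The primary MMRM (SAP 3.3.2) assumes that "the missingness of the observations may be dependent on the observed outcomes or covariates, but not on unobserved outcomes". It uses assessments in the Week 35 or Week 66 window and no more than 52 days after the last dose (SAP 3.2.1.1, 3.2.1.3, 3.3.1). The multiple-imputation analyses (SAP 3.3.3.2) run on the Safety Set and also accept in-window data beyond 52 days.

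**The concern.** Noncompliance is both a mandatory and a discretionary ground for leaving the study, and no threshold separates the two. Read literally, a patient who has stopped drug is encouraged to stay, while one who is still dosing but cannot meet every procedure has to go, even if willing to be assessed.

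The disease is staged by loss of ambulation (Protocol 2.1.1), and Appendix A adds 44 platelet collections to the tabulated visits. Inability to comply can therefore plausibly follow progression or poor tolerability. A Week 66 value lost for that reason may depend on the outcome that was not seen, which is what the MMRM assumes away. The loss is also avoidable, because the plan already has a set for handling deviations at analysis.

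**Working it through.** **1. Who loses a usable Week 66 value because of 8.9?** The visit windows are blacked out in the main SAP. The plan for the DSMB efficacy request (SAP 8.3, its Section 3.1.3) gives Days 209–269 for Week 35 and Days 411–501 for Week 66, with target Day 456. I assume the main SAP is similar.

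- *Still dosing, willing to be assessed.* An EOT assessment made at withdrawal between Day 270 (269 + 1) and Day 410 (411 − 1) falls in neither window and adds nothing to the MMRM. Had the patient stayed and kept dosing to Day 449, an assessment on Day 456 would be 7 days after the last dose and would count. Here 8.9 itself causes the loss.
- *Already off drug.* An assessment on Day 456 counts only if the last dose was on Day 404 or later (456 − 52). On the first window day it counts only if the last dose was on Day 359 or later (411 − 52). Protocol 6.1.3 also moves the EOT assessment to early termination. Retention would usually add nothing to the primary analysis. A Week 66 assessment would still feed the multiple-imputation analyses.
- *Unwilling to be assessed.* No wording of 8.9 yields a value.

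**2. FAS membership.** A withdrawn patient with a baseline and one post-baseline assessment stays in the FAS with Week 66 missing. Only a patient who leaves before any post-baseline assessment, and declines the one offered at withdrawal, drops out of it.

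**3. The plan's power.** Inputs from Protocol 10.2 and SAP 4: 135 patients at 2:1 (90 and 45), 25% dropout, two-sided 5% t-test; difference 9.6 and SD 14 (mNIS+7), difference 10.7 and SD 18 (Norfolk). Completers: 45 × 0.75 = 33.75 and 90 × 0.75 = 67.5.

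- mNIS+7: SE = 14 × √(1/33.75 + 1/67.5) = 2.95; 9.6/2.95 = 3.25; power 90.2% (normal), 89.6% (noncentral t).
- Norfolk: SE = 18 × √(1/33.75 + 1/67.5) = 3.80; 10.7/3.80 = 2.82; power 80.5% (normal), 79.7% (noncentral t).

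The stated 90% and 80% reproduce to within rounding. The documents do not say how many withdrawals under 8.9 to expect, or whether the 25% already includes them. For illustration only (noncentral t):

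| Dropout | mNIS+7 | Norfolk |
|---|---|---|
| 20% | 91.4% | 82.3% |
| 25% (plan) | 89.6% | 79.7% |
| 28% | 88.4% | 78.1% |
| 30% | 87.5% | 76.9% |

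**4. Bias, by assumption.** Suppose withdrawn active patients truly progress like placebo, while the model treats them like active patients. The overstatement is the share withdrawn times the planned effect: 5% × 9.6 = 0.48 and 10% × 9.6 = 0.96 points on mNIS+7; 0.54 and 1.07 on Norfolk.

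A simulation at the mNIS+7 planning values gives a different picture. It assumes a Week 35/66 correlation of 0.7, 20% random dropout, Week 35 means half those at Week 66, and removal probability proportional to exp((y66 − 16)/14). The estimator regresses Week 66 on arm and Week 35. The true difference is 9.6.

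| Extra removals | Both arms | Active only | Placebo only |
|---|---|---|---|
| 5% of patients | about 9.3 | about 10.2 | about 8.5 |
| 10% of patients | 9.0–9.1 | about 10.8 | about 7.2 |

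The one-arm shifts are somewhat larger if removals are drawn only from patients not already lost. With removals in both arms the shift of 0.3 to 0.6 points is at most about 0.2 of the SE (0.6/2.95). With 10% of patients removed from one arm only it is about 0.4 (1.2/2.95) or 0.8 (2.4/2.95) of the SE, in opposite directions.

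**The case against.** Much of the case against stands.

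- Only the ground of being unwilling or unable is mandatory; noncompliance and deviation are discretionary.
- Sections 8.8 and 8.9 govern different events, stopping drug and leaving the study. The Per-Protocol Set is an analysis subset and does not say who may be withdrawn. The sections pull in different directions but do not contradict each other.
- Section 8.9 encourages an EOT assessment at withdrawal. That is a real safeguard, but it stands in for Week 66 only if it falls in the window.
- The added weekly platelet draws may be done at home or at a local laboratory, so the travel burden is smaller than their number suggests.
- Sensitivity Analyses 4–7 apply multiple imputation under missing at random, copy increment from reference and jump to reference, and use withdrawal-visit data. The responder analysis counts a missing Week 66 as non-response. These analyses test the missing-data assumptions, but they do not recover observations that could have been made.

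A reader might infer that 8.9 turns the FAS into a Per-Protocol Set. It does not: the FAS has no compliance criterion, and most withdrawn patients remain in it. A reader might also infer that the sponsor could choose whom to remove with an eye to the result. The documents do not support that either, because the sponsor is blinded to treatment (Protocol 4.4) and has no post-baseline efficacy data before database lock (SAP 6).

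**Conclusion.** The point holds in a limited form and is a cheap improvement. Followed as written, 8.9 can end follow-up for a patient who is still dosing and willing to be assessed, on grounds that the plan otherwise uses only to define the Per-Protocol Set. The primary analysis then loses an obtainable Week 66 value for a reason that may be informative. For patients already off drug, the benefit of retention lies mainly in the multiple-imputation analyses.

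The size is unknown. It would be tempting to read the figures above as a forecast of lost power or of bias against or in favour of the drug. They are neither: the extra dropout, removal rates, correlation and mechanism are assumptions, and the direction changes with the arm that loses patients. The stated power does not depend on this point. The window argument assumes that the DSMB-request windows resemble the blacked-out ones.

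**What to change.** In Protocol 8.9, remove the grounds of being unwilling or unable to comply, noncompliance, and significant protocol deviation as reasons for withdrawal from the study. State that such patients remain in the study and complete the scheduled assessments they accept, including mNIS+7 and Norfolk QOL-DN at Week 35 and Week 66, with deviations handled through the Per-Protocol Set. Because 6.1.3 moves the EOT assessment to early termination, say explicitly that the Week 66 assessment is also sought from such patients once they are off drug.

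Leave withdrawal of consent, the investigator's discretion for medical reasons, the transplant rule and all dosing rules unchanged.

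Reconcile 8.9 with 8.5.4. The latter calls for weekly platelet monitoring for at least 6 weeks after the last dose, early-termination patients included. The former asks a withdrawn patient only for the EOT and early-termination assessments.

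The cost is protocol wording and a few more visits. These are already scheduled for patients still dosing; for those off drug, one Week 66 efficacy assessment is added to the early-termination one. No new procedure is needed.

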A An exception to the 6-week period given to perform the screening evaluations and baseline assessments is the TTR genotyping and amyloid biopsy tests. These tests may be conducted up to 10 weeks prior to Study Day 1. They are only conducted if appropriate documentation is not already available. In addition, ERG and ophthalmology examinations may be conducted up to 1-week after Study Day 1 if needed for scheduling purposes (except for Ile84 patients that fall under exclusion criteria 3 and should have eye examinations performed to determine eligibility).

B Patients that terminate treatment early should have the early termination visit and EOT efficacy assessments conducted ideally within 14 days from the last dose of Study Drug. They should then enter the post-treatment evaluation period.

Patients that discontinue treatment due to liver transplantation should return to the clinic for the EOT efficacy assessment as soon as feasible after the transplant procedures (if possible within 6 weeks). After the early termination and EOT efficacy assessment procedures are complete, the patient should be withdrawn from the study.

STUDY GLOSSARY

| Abbreviation/Acronym | Definition |
|------------------------------------|---|
| +7 | Sum 7 test. Includes measurements of nerve conduction, vibration threshold and heart rate to deep breathing |
| Alb/C ratio | Albumin/Creatinine ratio (performed on urine sample) |
| aPTT | Activated partial thromboplastin time |
| ASO | Antisense oligonucleotide |
| AUC | Area under the curve |
| BMI | Body mass index |
| CM | Cardiomyopathy |
| CM-ECHO Set | Patients with a diagnosis of TTR cardiomyopathy at study entry who are not in the ECHO subgroup, plus the patients in the ECHO subgroup |
| C-SSRS | Columbia-suicide severity rating scale |
| DSMB | Data and safety monitoring board |
| ECG | Electrocardiogram |
| ECHO | Echocardiogram |
| ECHO Subgroup | The subgroup of patients meeting protocol-specified ECHO criteria and having an additional echocardiogram assessment |
| EOT | End of treatment |
| ERG | Electroretinogram |
| ET | Early termination |
| FAC | Familial amyloid cardiomyopathy |
| FAP | Familial amyloid polyneuropathy |
| GLS | Global longitudinal strain |
| ICH | International conference on harmonization |
| IEC | Independent ethics committee |
| IRB | Institutional review board |
| IXRS | Interactive voice/web-response system |
| LLN | Lower limit of normal |

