6.1.4 Post-Treatment Period

After completion of the EOT efficacy assessment, patients will enter the 6-month post-treatment evaluation period and will report to the study center and have weekly platelet monitoring for a minimum of 6 weeks after the last dose of Study Drug which may be collected by the clinic, Sponsor's home healthcare service or by a local laboratory as outlined in the schedule of procedures (Appendix A). At Week 71, adverse events should be collected by the site personal through a phone contact with the patient if a clinic visit was not conducted.

Alternatively, after completion of the EOT efficacy assessment, eligible patients may elect to receive ISIS 420915 in an OLE study (ISIS 420915-CS3), pending study approval by the IRB/IEC and the appropriate regulatory authority. In this case, patients will not participate in the post-treatment evaluation period but weekly platelet monitoring should continue between the last dose of Study Drug in CS2 and the first dose of Study Drug in CS3. If this period extends beyond 6 weeks, the frequency will be determined by the Study Medical Monitor.

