8.5.4 Safety Monitoring Rules for Platelet Count Results

Platelets will be monitored weekly throughout the treatment period and for a minimum of 6 weeks after the last dose of Study Drug (this includes early termination patients as well as patients that complete the full 65-week treatment period). For patients participating in the Post-Treatment Evaluation Period, frequency of testing after the Week 71 visit will be determined by the Investigator in consultation with the Study Medical Monitor. For patients participating in the ISIS 420915-CS3 study, weekly monitoring should continue between the last dose of Study Drug in CS2 and first dose of Study Drug in CS3. If this period extends beyond 6 weeks, the frequency of monitoring will be determined by the Study Medical Monitor.

All platelet count results must be promptly reviewed by the Investigator to ensure that the count has not met the stopping rule.

If for any reason there is more than 14 days between platelet values (e.g., lab report of an unreadable sample due to clumping, hemolysis, or quantity not sufficient, or a missed lab assessment), the Investigator will contact the patient to hold dosing until a new platelet value is obtained and reviewed.

If a patient's platelet counts fall below $100,000/\text{mm}^3$, additional lab tests may be requested as determined by the Investigator in consultation with the Study Medical Monitor.

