Appendix A Schedule of Procedures *Continued*

Legend Continued

- 10 Weekly platelet monitoring is required throughout the treatment period and for a minimum of 6 weeks after the last dose of Study Drug (this includes early termination patients as well as patients that complete the full 65 week treatment period). For patients participating in the Post-Treatment Evaluation Period, frequency of testing after the Week 71 visit will be determined by the Study Medical Monitor in consultation with the Investigator. For patients participating in the ISIS 420915-CS3 study, weekly monitoring should continue between the last dose of Study Drug in CS2 and first dose of Study Drug in CS3. If this period extends beyond 6 weeks, the frequency will be determined by the Study Medical Monitor.

The following visits to collect platelet values are required in addition to the visits shown in the table. These visits do not have specified windows to allow flexibility of scheduling but with the intent that platelets are assessed each calendar week. Visits may be completed in clinic, by home healthcare service, or by a local laboratory:

Week 2, 4, 6, 7, 9, 11, 12, 14, 16, 17, 19, 21, 22, 24, 25, 27, 28, 30, 31, 33, 34, 36, 37, 39, 40, 42, 43, 45, 46, 48, 49, 51, 52, 54, 55, 57, 58, 60, 61, 63, 64, 66, 68, and 70

Time (time is in reference to Study Drug administration):

- A Pre-dose (during treatment period)
- B Pre-dose, 0.5, 1, 1.5, 2, 3, 4, 6, 8, 12, and 24-hour
- C Pre-dose, 3-hour
- D Pre-dose, 3 and 12-hour
- E Pre-dose, 24-hour, 3-day and 7-day
- F Pre-dose, 0.5, 1, 1.5, 2, 3, 4, 6, 8, 12, 24-hour, 3-day and 7-day. For both E and F: where applicable, the 7-day blood draw should be taken before the next weekly dose is given. The 12-hr blood draw is encouraged but optional.

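### Protocol 8.9 withdraws a liver-transplant patient once the end-of-treatment and early termination assessments are done; before day 42 after the last dose this conflicts with the required six weeks of platelet counts

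*Protocol*

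**What the plan says.** Two sets of instructions apply to a patient whose treatment ends because of a liver transplant.

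**Withdrawal.** Protocol Section 8.9 lists receipt of a liver transplant among the grounds on which a patient must be withdrawn. The end-of-treatment (EOT) efficacy assessment is to be completed "as soon as feasible after the transplant procedures (if possible within 6 weeks"), and then: "After the EOT efficacy assessment and early termination visit is complete, patients should be withdrawn from the study". The second paragraph of note B under the study design schema repeats this: "After the early termination and EOT efficacy assessment procedures are complete, the patient should be withdrawn from the study". Section 8.9 also asks for observations to be completed and reported up to the date of withdrawal.

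**Platelets.** Section 8.5.4 requires weekly counts during treatment and "for a minimum of 6 weeks after the last dose of Study Drug (this includes early termination patients", together with patients who complete treatment). Appendix A footnote 10 agrees: "Weekly platelet monitoring is required throughout the treatment period and for a minimum of 6 weeks after the last dose of Study Drug". On where the additional weekly samples are taken, the footnote says: "Visits may be completed in clinic, by home healthcare service, or by a local laboratory". Neither place makes an exception for transplant.

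For the other group that skips the post-treatment visits, those entering the open-label extension, Section 6.1.4 deals with the overlap directly: "patients will not participate in the post-treatment evaluation period but weekly platelet monitoring should continue". Section 8.9 and the transplant paragraph of note B contain no such sentence.

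**The concern.** The two clocks start at different events. The withdrawal clock starts at the transplant and has no lower limit, so a site that completes the assessments promptly also withdraws the patient promptly. The platelet clock starts at the last dose and runs for 42 days. When the first finishes before the second, withdrawal ends observation while counts are still required.

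What is at stake is safety monitoring. More frequent platelet counts were the main purpose of Amendment 9, which followed three severe thrombocytopenias in this study, one with a fatal intracranial bleed. The case that could be missed is a first platelet fall after an acceptable count at the early termination visit. There is also a small data consequence. The platelet abnormality summaries in the SAP use results up to the patient's last contact date (SAP Sections 3.2.1.4 and 3.9.4.2), so an early withdrawal shortens that record. The primary efficacy analyses and the power are not affected.

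**Working it through.** **Inputs**

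- Required platelet follow-up: weekly, at least 6 weeks = 42 days after the last dose (8.5.4; Appendix A footnote 10).
- Scheduled last dose: Week 65, Day 449 (Appendix A).
- Withdrawal point for transplant patients: when the EOT assessment and early termination visit are both complete (8.9; note B).
- Timing of those assessments: as soon as feasible after transplant, if possible within 6 weeks (8.9). No day relative to the last dose is given.

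**Reproducing the plan's own window.** 449 + 42 = 491, which is the Week 71 visit in Appendix A. Hematology is scheduled in the table at Weeks 67, 69 and 71, and footnote 10 adds platelet visits at Weeks 66, 68 and 70. That makes 6 weekly counts, so the schedule and the 6-week minimum agree.

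**Shortfall.** Let *d* be the day after the last dose on which both assessments are complete and the patient is withdrawn. Then

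uncovered days = max(0, 42 − *d*), and outstanding weekly counts = uncovered days / 7 for the days shown.

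| *d* (assumed) | Uncovered days | Weekly counts outstanding, of 6 |
|---|---|---|
| 7 | 35 | 5 |
| 14 | 28 | 4 |
| 21 | 21 | 3 |
| 28 | 14 | 2 |
| 35 | 7 | 1 |
| 42 or later | 0 | 0 |

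The table assumes that weekly counts were taken up to day *d*.

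**What determines *d*.** Write *d* = *g* + *e*, where *g* is the number of days from last dose to transplant and *e* the number from transplant to completed assessments. The documents do not give *g*, and they bound *e* only by the 6-week target. Over an assumed range, the outstanding weeks are max(0, 42 − *g* − *e*)/7:

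| | *e* = 14 | *e* = 28 | *e* = 42 |
|---|---|---|---|
| *g* = 0 | 4 | 2 | 0 |
| *g* = 14 | 2 | 0 | 0 |
| *g* = 28 | 0 | 0 | 0 |

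The conflict therefore arises only when the transplant closely follows the last dose and the assessments are done soon afterwards. Six of these nine assumed combinations show none.

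**The case against.** The strongest reply is that the requirement already exists. It is stated twice, was put in by Amendment 9 for this purpose, and names early termination patients. On that view 8.5.4 governs and nothing is missing but a cross-reference. Most of this stands: there is no gap in the platelet rule itself. It does not remove the conflict, because 8.9 is the specific instruction for transplant patients, places transplant among the mandatory grounds for withdrawal, and names the point at which withdrawal happens. A site reading both has no stated order of precedence.

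A second reply is that the residual risk is small. Patients with a confirmed stopping rule under 8.6.1 to 8.6.3 are directed into post-treatment follow-up (8.5). Serious adverse events and clinically significant laboratory abnormalities continue to be followed (9.4.1, 9.5.1), and the early termination visit includes one hematology sample. This also stands, and it is why the point is minor. A transplant team may well check platelets too, but the protocol does not route such results into the investigator review in 8.5.4 or the 24-hour notification in 8.6.3.

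Three stronger readings are tempting and are not supported.

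- A reader might infer that Section 8.8 has the same defect, since its minimum for a patient who declines post-treatment visits ("If the patient declines to participate in the post-treatment evaluation visits, at a minimum, the early termination visit and EOT efficacy assessment procedures") does not list platelet counts. That minimum is a floor. It neither waives nor contradicts 8.5.4, and it points to Appendix A, where footnote 10 requires the counts. Supposing that a site would misread it is conjecture.
- A reader might infer that early terminators in general lose their platelet follow-up. The first paragraph of note B sends them into the post-treatment period.
- A reader might try to size the exposure from exclusion criterion 13, which bars a transplant anticipated within 1 year of screening. An unanticipated transplant could fall in any dosing week, so the criterion does not measure the time at risk.

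**Conclusion.** The conflict is real, conditional and minor. If a transplant patient's EOT and early termination assessments are both complete before day 42 after the last dose, 8.9 and the transplant paragraph of note B direct withdrawal while 8.5.4 and footnote 10 still require counts. The size is set by the completion day, with day 14 and day 28 giving the 4 and 2 outstanding counts shown above. From day 42 onward the instructions agree.

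The completion day is an assumption throughout, since the documents fix neither the interval from last dose to transplant nor that from transplant to assessment. The number of patients affected is likely small but cannot be estimated, and the documents do not say when platelet falls occur after dosing stops. The case for a change rests on the seriousness of the hazard and the low cost of the correction.

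**What to change.** Change only the transplant paragraph of Section 8.9 and the transplant paragraph of note B. Add to each:

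*For liver-transplant patients, weekly platelet monitoring per Section 8.5.4 continues until at least 6 weeks after the last dose of Study Drug (clinic, home healthcare or local laboratory). Withdrawal takes effect once this monitoring and the assessments above are complete, unless the patient withdraws consent or is unable to comply.*

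Limiting the sentence to transplant patients, with the two exceptions, keeps it from delaying withdrawal on the other grounds in 8.9. It follows the approach already taken for open-label extension patients in 6.1.4.

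No new test is introduced, because 8.5.4 already requires the counts and footnote 10 already allows them outside the clinic. The cost is up to 6 more weeks of limited contact for a few patients, during which adverse events and concomitant therapy would still be recorded. With the change, the shortfall is 0 counts for any assessment date, provided the patient stays in contact.
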